Legal guardians of children who are not influenza vaccine-eligible including children less than 6 months of age, children on immunosuppressive medications, and children with underlying medical conditions resulting in an immunocompromised state.

Sample Size:

Specific Aim 1: baseline vaccine hesitancy is 25%⁴⁷. Clinically meaningful difference in hesitancy is defined as 15%. This difference can be detected with 80% power with 250 subjects per group.

Specific Aim 2: We anticipate our intervention could reduce vaccine hesitancy from the national baseline of 25% to 15% on the post-intervention survey. Identifying this reduction from 15% to 15% in paired proportions with 80% power requires enrollment of 312 subjects who complete both tests (i.e. enrolling 312 subjects identified as vaccine-hesitant).

Exploratory Aim: Motivational interviews with study subjects (20) and study volunteers (4) will not be powered or statistically analyzed.

Interventions and Interactions

We will conduct a prospective cohort study of families with children aged 6 months and up who are eligible to receive the seasonal influenza vaccine. Subjects who consent to this study will answer questions which will include demographic questions, a baseline 20-item Altruism Scale, and an 8-item Vaccine Hesitancy Scale. The 20-item Altruism Scale will be scored based on a 5-point Likert scale, with each question scoring from 1-5, then added together to give a cumulative score. Higher scores indicate higher altruism. The Vaccine Hesitancy Scale will be scored as previously described: scoring responses for each item will be scored as follows: strongly agree = 1, agree = 2, disagree = 4, and strongly disagree = 5, such that higher values always indicated greater hesitancy. We will then calculate the average score of the 8 items included in the scale, and use the pre-defined average score of ≥ 3 as "hesitant." Subjects identified as vaccine-hesitant based on a Vaccine Hesitancy Score ≥ 3 will be given an educational handout and provided a standardized, brief educational session overviewing the educational handout. At the end of the doctor's visit, subjects will complete a second identical 8-item Vaccine Hesitancy Scale.

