Following study volunteer participation and subject participation in the study, up to four study volunteers and up to 20 vaccine-hesitant study subjects will be contacted by [name], PhD, to request an interview. The interviews will take place virtually, by phone or video, by [name]. Study subjects will have already provided written consent to this interview, but [name] will review the purpose of this phone call and provide an opportunity for study subjects to opt out. All study volunteers will be provided a Study Information Sheet when they orient as study volunteers on this project, which details the purpose of the research project and that up to four of the volunteers, [name] will review/re-provide a Study Information Sheet, detailing the purpose of the interview, but there will be no written consent for the study volunteers.

Analytical Plan

For Specific Aim 1, our primary outcome is vaccine hesitancy, which is dichotomized as hesitant (mean score \geq 3) or not hesitant (mean score \leq 3) based on results of the Vaccine Hesitancy Scale. Exposures will

include general demographic and clinical characteristics along with the Self-Report Altruism Scale (expresses as a continuous score from 20 to 100). The children's clinical status will be categorized using the Pediatric Medical Complexity Algorithm v3.1⁴⁹. Results will be analyzed initially using descriptive statistics to determine the prevalence of hesitancy. Associations between hesitancy and potential exposures will be assessed using chi square or ANOVA. Associations found to be statically significant in the bivariate analysis will be incorporated into a mixed-effects multivariable logistic regression model, which will treat practice location as a random effect. A p value of 0.1 will be used for inclusion of variables in the model; otherwise, a p value <0.05 will be the cutoff for statistical significance.

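### The Aim 2 pairing of 312 completers with 80% power depends on an unstated, extreme discordance assumption that cannot hold when every subject is hesitant at baseline

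*Combined protocol and SAP*

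**What the plan says.** All of the Aim 2 sizing is in the Sample Size section of the combined protocol and SAP.

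- The expected effect: "We anticipate our intervention could reduce vaccine hesitancy from the national baseline of 25% to 15% on the post-intervention survey".
- The next sentence restates that effect as "Identifying this reduction from 15% to 15% in paired proportions" and attaches 80% power and 312 completers to it: "in paired proportions with 80% power requires enrollment of 312 subjects who complete both tests".
- The same sentence defines those completers in brackets: "i.e. enrolling 312 subjects identified as vaccine-hesitant".

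The section gives no discordant proportion, within-person correlation, alpha, sidedness or dropout. The only significance level is in the Aim 1 paragraph of the Analytical Plan: "otherwise, a p value <0.05 will be the cutoff for statistical significance".

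Under Interventions and Interactions, only guardians with a mean score of at least 3 receive the handout and session. They then repeat the same eight-item scale at the end of the same visit. For Aim 2 the Analytical Plan makes the change in score the primary outcome, tested by a paired t-test or Wilcoxon signed-rank test.

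**The concern.** Before and after rates are marginal proportions, and two margins do not fix a paired sample size. The size also depends on how many people change in each direction, and the plan does not say. A reader therefore cannot get from 25% and 15% to 312 without supplying an assumption. The assumption that reproduces 312 has a sizeable share of subjects moving from not hesitant to hesitant after the education. That sits badly with an identical survey repeated within one visit, and worse with a cohort made up only of hesitant guardians.

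What is at stake is the meaning of the only recruitment target given for Aim 2. A reader will take 312 as the number that secures 80% power for this study's comparison, and it needs to be clear whether it does.

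**Working it through.** **Inputs**

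- Fall from 25% to 15%, so d = 0.10; power 80%; 312 completers (Sample Size, Specific Aim 2).
- Alpha 0.05 (Analytical Plan, Aim 1 paragraph; none is given for the sizing).
- Two-sided test: my assumption, as sidedness is not stated.
- Discordance or correlation: not stated, so the whole possible range is shown.

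**Step 1. Reproduce 312.** Let p10 be the share going from hesitant to not hesitant, p01 the reverse, p11 the share hesitant both times, ψ = p10 + p01 and d = p10 − p01. The McNemar normal-approximation formula is

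n = [1.960 √ψ + 0.8416 √(ψ − d²)]² / d².

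With p10 = 0.25 and p01 = 0.15, ψ = 0.40:

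n = [1.960 × 0.6325 + 0.8416 × 0.6245]² / 0.01 = (1.2396 + 0.5256)² / 0.01 = 311.6, rounded up to 312.

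This matches the plan exactly. The one-sided version gives 246.

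**Step 2. Read 25% and 15% as margins.** Then p10 = 0.25 − p11 and p01 = 0.15 − p11, so ψ = 0.40 − 2 p11. With within-person correlation φ, p11 = 0.25 × 0.15 + φ √(0.25 × 0.75 × 0.15 × 0.85) = 0.0375 + 0.1546 φ. Since p11 lies between 0 and 0.15, φ lies between −0.24 and 0.73. Power at 312 is Φ{[0.10 √312 − 1.960 √ψ] / √(ψ − 0.01)}.

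| φ | p11 | ψ | pairs for 80% power | power at 312 |
|---|---|---|---|---|
| −0.24 | 0 | 0.400 | 312 | 80% |
| 0 | 0.0375 | 0.325 | 253 | 87.6% |
| 0.3 | 0.0839 | 0.232 | 180 | 95.9% |
| 0.5 | 0.1148 | 0.170 | 132 | 99.2% |
| 0.73 | 0.15 | 0.100 | 77 | above 99.9% |

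The discordant cells of Step 1 are the first row. There p11 = 0: every hesitant guardian converts, and 15% of all subjects become newly hesitant.

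**Step 3. Apply the stated cohort.** If all 312 are hesitant at the first survey, the baseline margin is 100%, p01 = 0, and φ is undefined. The p01 = 0.15 that yields 312 cannot occur. No row of the table describes this cohort, because every row has a 25% baseline.

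**Step 4. What 312 does give here (illustration).**

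- Paired score analysis, two-sided 5%, 80% power, normal approximation: detectable mean change = (1.960 + 0.8416) / √312 = 2.8016 / 17.664 = 0.16 standard deviations of the change.
- Share converting to not hesitant: the 95% half-width is widest at 50%, 1.96 × √(0.25 / 312) = 0.055, or 5.5 percentage points.

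**The case against.** The strongest reply is that 312 is a legitimate answer. Cells of 0.25 and 0.15 with p11 = 0 form a valid table whose margins are exactly 25% and 15%. With no correlation stated, taking the largest size in the range protects power at every correlation. This stands. A reader might infer that 312 is an arithmetic error, or that the study is too small for the test described. The documents support neither: by the normal-approximation test, 312 gives about 80% power at worst. An exact McNemar test gives slightly less, 77.8% in the extreme case and 86.0% under independence.

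It is also fair to say that the source of 312 is inferred. The continuity-corrected formula gives 312 at ψ = 0.375, and 250 / 0.8 = 312.5, although no dropout is stated. The exact match with the text's own two percentages makes swapped cells likely but does not prove it.

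Finally, an over-large sample in a pilot brings no bias and no loss of power. That is true and limits the seriousness. It does not rescue the power statement, since Step 3 shows that the table behind it cannot arise in the cohort defined in the same sentence.

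**Conclusion.** The point holds as a matter of unstated and inapplicable assumptions. The number itself is not too small. For a fall from 25% to 15% in a mixed sample, 312 is the top of a range from 77 to 312. It matches 80% power only at a correlation of −0.24, which is implausible for an identical survey repeated at the same visit. At any non-negative correlation 77 to 253 pairs would do, and 312 would give 88% power or more. In the cohort the plan defines, none of these figures applies, so 80% power is not a property of this design. Separately, a fall of 15% to 15% is a zero difference, for which no finite sample size exists; it is plainly a slip.

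Two further inferences should be resisted. One is that 253 is the conservative replacement. Independence is not the worst case, and 253 pairs would have about 71% power at ψ = 0.40. The other is a comparison of screening loads made by dividing 312 and 253 by the 25% prevalence. The division treats all those counted as hesitant at baseline, while 253 was derived for a sample in which only a quarter are.

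The figures assume a two-sided 5% test and, except where marked exact, the normal approximation without continuity correction.

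**What to change.** In the Sample Size section, Specific Aim 2:

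1. Correct the fall written as 15% to 15%.
2. Remove the statement that 312 is required for 80% power on a fall from 25% to 15%.
3. Keep 312 as the target if wished, and state the power or precision it gives for the hesitant-only cohort and the planned paired score analysis. Give the assumed standard deviation of the change, or the assumed conversion rate, with alpha and sidedness. The figures in Step 4 show the form this could take.
4. If the paired-proportions calculation is kept as an illustration, state the discordance assumed and show the range from 77 to 312. Do not substitute 253 as a conservative figure.

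The cost is a few rewritten sentences, with no extra subjects and no change to study conduct. The one new input is a standard deviation of change or a conversion rate, which the documents do not supply. It would have to be entered as a stated assumption with a range.

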Promoting Altruism to Enhance Vaccine Acceptance NCT04568590 Study Protocol and Statistical Analysis Plan Document Date: 6/27/22

Cohort Study to Determine the Effect of an Educational Intervention Focusing on Herd Immunity to Enhance Vaccination Uptake Rates

Principal Investigator(s), Resident Investigator:

[name], MS, Co-Principal Investigator [name], Co-Principal Investigator [name], DO, Resident Investigator

Sponsor or Funding Source: Center for Vaccines at the Extremes of Aging Pilot Funds

Background, Rationale, and Context

Vaccine hesitancy is on the rise in the United States, which is causing a resurgence of vaccine-preventable diseases. Vaccine hesitancy regarding the seasonal influenza vaccine is especially prevalent, with a recent study indicating hesitancy prevalence of 6.1% for routine childhood vaccines but 25.8% for influenza vaccine¹⁻⁶. This trend is particularly concerning today as the world awaits a COVID-19 vaccine, the effectiveness of which will be critically threatened by poor uptake due to vaccine hesitancy. Uniform strategies to address vaccine hesitancy have met challenges due to pervasive online misinformation, and the heterogeneity of the vaccine-hesitant community, which crosses racial, socioeconomic, educational, and political lines^{3, 7-26}. However, a common thread that globally may contribute to vaccine hesitancy is rising individualism, the moral stance that the individual takes precedence over a larger social group²⁷⁻²⁹. Altruistic, prosocial motivation seems to be an essential component of vaccine acceptance³⁰. Altruism has also been identified as the major motivator in subjects willing to participate in preventative vaccine trials³¹. One potential strategy to increase altruism amongst vaccine hesitant individuals is to provide education on the concept of herd immunity. A recent scenario study found that explicitly communicating the role of herd immunity increased people's intention to accept vaccines, especially in Western, individualist cultures³². Strategies like this to promote altruism in order to enhance vaccine uptake could improve public health outcomes. How to best communicate the benefits of herd immunity in an increasingly individualistic, nationalistic climate is unclear but must be addressed.

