Pediatric oncology patients represent a potentially excellent population on whom to base a herd immunity educational effort aimed at enhancing altruism in vaccine-hesitant parents: pediatric cancer patients tend to elicit strong sympathetic responses from the public; they come from all communities in the US and are therefore local; and they rely on herd immunity for protection from vaccine-preventable infections because they are largely unable to receive vaccines due to their immunocompromised state³³⁻⁴⁶. Therefore, we hypothesize that a brief educational encounter on herd immunity focusing on local pediatric cancer patients' risk and sponsored by local pediatric oncology providers will increase altruism scores and directly correlate with an increase in seasonal influenza vaccine acceptance. We aim to explore the overall effectiveness of this educational intervention, and also aim to explore whether there may be an identifiable subpopulation most amenable to this type of intervention based on baseline altruism score, race, educational level, or political affiliation.

Objectives

Specific Aim 1: To identify associations with influenza vaccine hesitancy, including parental demographics and altruism score, in families with healthy children attending two pediatric practices.

Specific Aim 2: In the cohort of families with baseline vaccine hesitancy, to assess the effectiveness of a pilot educational intervention focusing on the development of herd immunity for pediatric oncology patients by measuring:

- a. The change in vaccine hesitancy scores pre- and post-intervention.
- b. The change in the score of question number 6 on the Vaccine Hesitancy Scale, which uniquely and specifically relates to altruism. We will also compare the change in this individual score

with the change in the other individual question scores, which relate to other realms of vaccine confidence, including safety, efficacy, and trust.

c. The rate of influenza vaccine uptake compared to historic controls from previous influenza seasons.

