Exploratory Aim: In an effort to further understand the complex interaction between study volunteers (interviewing medical students) and study subjects, including how unique interactions between the study representative(s) and the study subjects may affect questionnaire responses and vaccine acceptance decisions, we aim to conduct motivational interviews with 20 vaccine-hesitant participants, and with four study volunteers. Each motivational interview will be conducted by [name], PhD, Associate Professor and Chair of the Department of Communication at Wake Forest University.

We aim to explore the relationship between baseline influenza vaccine hesitancy rates and baseline altruism scores. Effectiveness of our intervention is dependent on parental altruism levels; therefore, we also seek to determine if there is an association between parental altruism and vaccine hesitancy for their children.

Methods and Measures

Setting:

Study subjects will be recruited from two Wake Forest University Baptist Medical Center general pediatric practices: Westgate Pediatrics and Pediatrics - Ford, Simpson, Lively, and Rice. Westgate Pediatrics is located at [name]. Westgate serves a diverse population, with approximately 50% of patients receiving Medicaid services. Pediatrics - Ford, Simpson, Lively, and Rice is located at [name]. This latter practice serves a large population that is generally of a higher socioeconomic status than Westgate Pediatrics, with approximately 25% of patients receiving Medicaid services. Study volunteers will be Wake Forest School of Medicine medical students in their 4th year who volunteer to participate in this project as credit for a 4th year elective rotation.

Design:

A single-arm prospective cohort study will be conducted. The study will enroll as study subjects legal guardians of children who are influenza vaccine-eligible to measure their vaccine hesitancy scores, altruism scores, and the impact of an educational intervention focused on herd immunity on the guardians' vaccine hesitancy score.

Inclusion Criteria:

All legal guardians of children aged 6 months and up who are influenza vaccine-eligible and present to the pediatric clinic.

Exclusion Criteria:

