We will also conduct a retrospective chart review of all patients who participated in the initial survey to determine whether the child received the influenza vaccine. Retrospective chart review will also be conducted to estimate the influenza vaccine acceptance rates for each pediatrics practice over the same time period from one year prior.

Two study volunteers will be at each pediatric clinic. A volunteer will approach an eligible parent/guardian in the waiting room prior to their scheduled appointment and obtain informed consent to participate in the study. A consenting subject will complete the Vaccine Hesitancy Scale⁴⁷ orally with the study volunteer. The Vaccine Hesitancy Scale is positive if the average of all questions is greater than or equal to 3. When the study volunteer is inputting and grading the Vaccine Hesitancy Scale in a REDCap survey tool on an iPad, the subject will complete the Self-Report Altruism Scale⁴⁸ and several demographic questions on paper. If the guardian screens positive for vaccine hesitancy (i.e., vaccine hesitancy score average \geq 3), they will be given the informational handout along with a brief script. The parent will have the opportunity to review the intervention in the waiting room and during the visit while the provider is out of the room. If the guardian was deemed vaccine hesitant and was given the intervention, the study volunteer will remain at the nurse's station and wait for the visit to be completed. Once the family is finished, the study volunteer will approach the participant once again and complete the Vaccine Hesitancy Scale orally prior to check out. The subject's child's electronic health record will then be accessed to document whether that patient received the seasonal influenza vaccine that day.

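### Aim 2c appears to assess uptake in hesitant families, but the only historic control described is each practice's prior-year rate, not restricted to or adjusted for hesitancy

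*Combined protocol and SAP*

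**What the plan says.** The stem of Specific Aim 2 (Objectives) fixes the population: "In the cohort of families with baseline vaccine hesitancy, to assess the effectiveness of a pilot educational intervention". Item c under that stem is "The rate of influenza vaccine uptake compared to historic controls from previous influenza seasons".

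Interventions and Interactions says that only guardians with a mean Vaccine Hesitancy Scale score of 3 or more receive the handout and short session. The same section plans two chart reviews. One covers every child whose guardian took the initial survey, to see whether the child was vaccinated. The other is to "estimate the influenza vaccine acceptance rates for each pediatrics practice over the same time period from one year prior". The scale is given to consenting subjects during the study, and no hesitancy score for prior-year patients is described.

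In the Analytical Plan, the paragraph on Specific Aim 2 makes uptake a secondary outcome, compared qualitatively with historic controls. It does not restate which families are counted, and it describes no restriction, matching or adjustment of the historic rate.

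**The concern.** The hypothesis in the Background is that the session "will increase altruism scores and directly correlate with an increase in seasonal influenza vaccine acceptance". Uptake is the only measure of vaccination behaviour in the plan, so Aim 2c carries that part of the hypothesis.

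The Background also takes hesitancy to depress uptake. It says so of a future COVID-19 vaccine, whose effectiveness would be "critically threatened by poor uptake due to vaccine hesitancy". If the same holds for influenza vaccine in these two practices, hesitant families start below the practice average. Setting their uptake after the handout beside the practice rate then mixes two things: what the handout did, and how far below average these families already were. A qualitative comparison has no step that removes the second.

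**Working it through.** The plan gives no expected uptake, effect size or sample size for this comparison, so there is no figure to reproduce. The check is an identity.

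**Inputs**
- h, the proportion hesitant. Sample Size says that the intervention "could reduce vaccine hesitancy from the national baseline of 25% to 15% on the post-intervention survey". The Background gives "hesitancy prevalence of 6.1% for routine childhood vaccines but 25.8% for influenza vaccine". Both are national figures; neither describes these practices.
- u_N and u_H, uptake in non-hesitant and untreated hesitant families. The documents give neither. Write g = u_N - u_H; every value of g below is an assumption.
- t, the true gain in hesitant families. Also assumed.

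**Conditions:** no season trend, the same h in both years, enrolled families like the practice, and the same uptake window.

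**Hesitant cohort against the practice rate**

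Practice rate = (1 - h)u_N + h·u_H

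Apparent effect = (u_H + t) - practice rate = t - (1 - h)g

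With t = 10 points and h = 25%:

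| Assumed gap g (points) | Apparent effect (points) |
|---|---|
| 0 | 10 - 0.75 × 0 = +10.0 |
| 5 | 10 - 0.75 × 5 = +6.25 |
| 10 | 10 - 0.75 × 10 = +2.5 |
| 13.3 | 10 - 0.75 × 13.3 = 0 |
| 20 | 10 - 0.75 × 20 = -5.0 |

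In rates: suppose 70% of non-hesitant and 50% of hesitant families vaccinate. The practice rate is 0.75 × 70 + 0.25 × 50 = 65%. If hesitant uptake rises to 60%, the comparison shows 60 - 65 = -5 points.

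Gain hidden per 10 points of gap, (1 - h) × 10: 8.5, 7.5 and 6.5 points at h = 15%, 25% and 35%.

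Gap at which a real gain looks null, t/(1 - h), at h = 25%: 6.7, 13.3 and 20.0 points for t = 5, 10 and 15. For t = 10 it is 11.8 at h = 15%, 13.5 at h = 25.8% and 15.4 at h = 35%.

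**All surveyed families against the practice rate**

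Apparent effect = [(1 - h)u_N + h(u_H + t)] - practice rate = h·t = 0.25 × 10 = 2.5 points, if the enrolled mix matches the practice and untreated families do not change.

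**Hesitant children against their own prior season**

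The gap term drops out. The 95% half-width is 1.96 × √[(d - t²)/n], where d is the assumed proportion of children whose status changes and t = 0.10:
- n = 312 (the plan's number of hesitant completers): 5.4 points at d = 25%, 6.9 at d = 40%.
- n = 0.70 × 312 = 218, if 30% had no prior-season visit: 6.5 and 8.3 points.

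This comparator has biases of its own. Subjects are guardians of children "who are influenza vaccine-eligible and present to the pediatric clinic", so every enrolled child has a visit this season but may not have had one last season. If 10% to 30% had none and their prior uptake was 10 to 30 points lower, the spurious gain is 0.10 × 10 = 1 to 0.30 × 30 = 9 points. If 10% to 30% became hesitant since last season and their prior uptake was 10 to 30 points higher, 1 to 9 points of gain are hidden.

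**The case against.** **The population may be all surveyed families.** The two chart reviews stand side by side, the first covers every participant, and the uptake sentence in the Analytical Plan names no population. This stands as a possible reading. The Aim 2 stem, and the place of the uptake sentence in the Aim 2 paragraph, favour the hesitant cohort. On the other reading the fault becomes dilution, so neither reading isolates the handout's effect.

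**The offset is one component among several.** Season trend, consenting attendees against all practice patients, vaccination on the visit day against vaccination over a period, and an undefined denominator for the practice rate could act either way. This stands. It makes the net error uncertain; it does not make the comparator suitable.

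**The consequence is limited.** The outcome is secondary and qualitative in a pilot, and any historic comparison in a single-arm study is weak. This stands, and it bounds the importance of the point. The hesitancy mismatch is still an avoidable addition to that weakness.

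**The replacement may be no better.** Its possible bias of 1 to 9 points in either direction is similar to the 7.5 points hidden by a 10-point gap. This stands as a reason to show both comparisons and to treat neither as an unbiased estimate. What the replacement removes is the structural difference between hesitant families and the practice as a whole.

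**Conclusion.** The point holds in conditional form. No section supplies a historic rate restricted to or adjusted for hesitancy, and on the better reading the Aim 2c group is selected for hesitancy. Other things equal, the offset is -(1 - h)g: 7.5 points per 10 points of gap at h = 25%, with a 10-point gain looking null at a gap of 13.3 points.

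A reader might infer that the plan will understate a real gain, or show a fall where there was a rise. The documents do not support that. They give no uptake rate for any group, their premise that hesitancy lowers uptake is stated for COVID-19 vaccine, and the other differences could offset the gap. A reader might also infer that the text settles the population beyond doubt; it does not.

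The primary paired analysis of score change is unaffected. The plan should be changed because uptake is its only behavioural outcome and the change is cheap.

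**What to change.** 1. In the Analytical Plan, state that the Aim 2c population is the hesitant cohort.
2. In the chart review already planned, also record each enrolled child's prior-season vaccination date, prior-season eligibility, whether there was a prior-season visit in the same window, and the current-season vaccination date relative to the study visit.
3. Report hesitant children's uptake against their own prior-season uptake, with the same definition and calendar cut-off in both seasons and a 95% CI. Repeat it in those with a prior-season visit. Label it an uncontrolled before-after comparison that may be biased either way, with an interval that covers sampling error only. Report separately children vaccinated before the study visit, whose doses cannot be credited to the handout.
4. Report current uptake separately for hesitant and non-hesitant participants. This makes the difference between the groups visible, although it does not supply a hesitant-only historic rate.
5. Keep the practice-wide rate as context, with no inference about effectiveness drawn from it.

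While editing, reconcile the plural previous seasons in Aim 2c with the single prior year in Interventions and Interactions, and the two uptake definitions in that section (visit day only, and no day limit).

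Cost: a few extra fields on charts already being opened, and a wider interval in the visit-restricted result. The Informed Consent section includes permission to access the child's record; the sponsor should confirm that this covers the prior season.

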For Specific Aim 2, our primary outcome will be the change in vaccine hesitancy scores pre- and postintervention, which will be assessed with a paired t-test or Wilcoxon signed-rank test, following review of the score distribution. We will also measure the change in Question #6 (the only Altruism-specific question on the questionnaire) independently, and also compared with each other individual question on the questionnaire, and pre- and post-intervention change will be assessed with a paired t-test or Wilcoxin signranked test, following review of the score distribution. As a secondary outcome, the rate of influenza vaccine uptake will be compared qualitatively to historic controls.

For the Exploratory Aim, we will capture qualitative data and seek trends. No statistical computation will be done on these data.

All data will be entered directly into a Research Electronic Data Capture database and analyzed using SAS v9.4 (Cary, NC).

Human Subjects Protection

Risks for participation are not more than minimal. There is risk of accidental unauthorized release of identifiable personal information. Data access will be limited to study staff. Data and records will be kept locked and secured, with any computer data password protected. Participation in a post-study interview by the study volunteers will not require written consent, but it is voluntary. The grading for the elective course is Pass/Fail, and will be exclusively based on their participation in the actual study, and not the post-study interview, which is voluntary.

Subject Recruitment Methods

All parents who present to either pediatric clinic with children 6 months and up who are eligible for the flu vaccine will be eligible to participate in the study. Two student volunteers will be at each clinic for the recruitment process during flu season (between October and December depending on volunteer schedule availability). A volunteer will approach any parent(s) in the waiting room prior to their schedule appointments to recruit for the study regardless of gender or race/ethnicity.

For the retrospective chart review, there is minimal risk involved to participants. All protected health information will be de-identified prior to data analysis and publications; subject identity will be known only to the study staff. Subjects who participated in the initial arm of the study will be included in the chart review to determine further demographic data and whether the child received the flu vaccine.

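### The Aim 2 primary outcome is re-asked aloud by the study volunteer after the education, so any added pressure to agree would probably count as benefit; self-completion at both time points would cheaply reduce this risk.

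*Combined protocol and SAP*

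**What the plan says.** Interventions and Interactions sets out the visit. A volunteer obtains consent in the waiting room, and the guardian completes the Vaccine Hesitancy Scale "orally with the study volunteer". The volunteer enters and grades it in REDCap on an iPad. In the meantime "the subject will complete the Self-Report Altruism Scale" and several demographic questions on paper. Guardians who screen as hesitant go on to the education: "they will be given the informational handout along with a brief script". The volunteer waits at the nurse's station during the visit, and afterwards "the study volunteer will approach the participant once again and complete the Vaccine Hesitancy Scale orally prior to check out". On staffing, "Two study volunteers will be at each pediatric clinic".

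Under Design, "A single-arm prospective cohort study will be conducted". For Specific Aim 2 the Analytical Plan states that "our primary outcome will be the change in vaccine hesitancy scores pre- and postintervention, which will be assessed with a paired t-test or Wilcoxon signed-rank". The choice between the two is left until the score distribution has been reviewed. Question 6, the altruism item, is analysed separately in the same way.

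The Exploratory Aim, under Objectives, recognises that interactions between study representatives and subjects "may affect questionnaire responses and vaccine acceptance decisions". The response is a set of interviews with up to 20 hesitant guardians and up to four volunteers. The Analytical Plan treats these as qualitative, with no statistical computation.

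**The concern.** The primary measurement comes right after a persuasive appeal about local children with cancer. The guardian must answer the same eight questions aloud to a representative of the study that made the appeal. A guardian whose views have not changed may still soften an answer out of courtesy.

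This pressure exists only at the second asking, so it enters the change score. Its likely direction is toward lower hesitancy, which is what the study hopes to see. With no control arm, nothing in the analysis separates it from a real change of view. It could also concentrate on Question 6, the item closest to the message, and so imitate the hypothesised mechanism.

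The protocol anticipates that these interactions can affect answers, but addresses this only through the qualitative interviews. It describes no self-completed post-test, independent assessor or sensitivity analysis for the primary score.

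**Working it through.** **1. The planned number.** Sample Size gives 312 hesitant guardians completing both tests, at 80% power for paired proportions. The McNemar formula reproduces this with 0.25 and 0.15 as the two discordant cells, so ψ = 0.40 and d = 0.10, at two-sided alpha 0.05 (sidedness is not stated, so two-sided is assumed):

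n = [z(0.975)·√ψ + z(0.80)·√(ψ − d²)]² / d² = [1.960·√0.40 + 0.842·√0.39]² / 0.01 = [1.240 + 0.526]² / 0.01 = 311.6, rounded up to 312.

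The point here does not depend on how 312 was reached. It is only the n used below.

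**2. What a paired test on scores can detect at n = 312.** (1.960 + 0.842)/√312 = 2.802/17.66 = 0.159 SD of the change score, with 80% power. A small systematic shift is therefore enough to produce a significant result.

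**3. What one softened item does.** Items score 1, 2, 4 or 5, and the scale is the mean of 8 items (Interventions and Interactions). Moving one item from disagree (4) to agree (2) lowers the mean by (4 − 2)/8 = 0.25. If a share s of guardians does this, the group mean falls by 0.25·s.

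**4. Chance of a significant result with no true effect.** The normal approximation to the paired test is:

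P = Φ(δ − 1.96) + Φ(−δ − 1.96), with δ = 0.25·s·√312 / SD.

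The documents give neither s nor the SD of change. Both are assumed, and both are varied:

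| Share moving one item | Fall in mean | SD 0.5 | SD 0.6 | SD 0.8 |
|---|---|---|---|---|
| 0% | 0 | 5% | 5% | 5% |
| 10% | 0.025 | 14% | 11% | 9% |
| 20% | 0.05 | 42% | 31% | 20% |
| 40% | 0.10 | 94% | 84% | 60% |

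Worked cell (20%, SD 0.6): δ = 0.05 × 17.66/0.6 = 1.472. Φ(1.472 − 1.96) = Φ(−0.488) = 0.313, and the opposite tail adds less than 0.001.

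**5. What cancels and what does not.** Let the interviewer effect be a at baseline and a + c after the education. The change score then contains (a + c) − a = c. The part common to both oral sessions drops out, and only the added pressure c remains. The table shows the consequence of c. It does not show how much of c comes from asking aloud, nor how much self-completion would remove.

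**The case against.** Baseline and post-test are already matched in mode, so ordinary interviewer bias subtracts out. This stands, and it limits the point to the pressure added by the education.

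Much of that pressure comes from repeating an identical scale in the same visit without a control. A form handed over and collected by study staff keeps some of it. This also stands: self-completion is a reduction, not a cure.

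The illustration depends heavily on an unsourced share. At SD 0.6 the result runs from 11% to 84% as the share goes from 10% to 40%, so no single figure should be quoted as the bias.

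The interviews, and same-day vaccination taken from the health record, can be said to limit reliance on the score. Vaccination is indeed free of this effect. But it is secondary and compared only qualitatively with historic controls, and the interviews correct nothing. Neither protects the primary outcome.

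A reader might infer three stronger things that the documents do not support:

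- That the person who educates is definitely the person who re-asks. The sentences on the handout and session are passive. The volunteer is the natural reading because no other study person is described at that step.
- That the re-asking comes within minutes. The text says only after the visit and before check-out.
- That bias is established. The Exploratory Aim says interactions may affect answers and gives neither direction nor size.

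Lack of blinding adds little as a separate criticism, since everyone post-tested has had the education.

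**Conclusion.** The concern holds as a risk of bias in the Aim 2 primary outcome, probably toward benefit and of unknown size. It rests on three features of the plan: oral re-administration by the volunteer in the same visit after the education, a primary outcome defined as the pre/post change, and no control arm. The direction is a judgement about how people answer after an appeal; the documents do not state it.

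On the assumptions tabulated, a shift confined to one item could raise the chance of a falsely significant result from 5% to anywhere between 9% and 94%. That range shows the primary test is sensitive to small courtesy shifts. It does not estimate the bias in this study. The change is worth making because self-completion is already part of the same visit, so it is cheap.

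**What to change.** Have guardians complete the 8-item scale themselves at baseline and again before check-out, on the REDCap iPad with automatic scoring or on paper. Offer oral help only on request, and record the mode at each time point. Change both administrations together: changing only the second would mix a mode difference into the change score.

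Having the clinic's other volunteer ask only the post-test is not a good substitute. The interviewer would then differ between pre and post, and that person still represents the study.

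The cost is a small change in workflow, with a few more skipped items or requests for reading help. Automatic scoring on the iPad could replace the volunteer's entry and grading step. The planned 312 does not change. The report should still say that some demand effect may remain in the change score.
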